Thus, to be included in the study, all subjects will have at least 12 months in both the Pre and Post periods. We selected a follow-up period of up to three years because we hypothesized that patients in HSA-HDHPs with PDLs might experience benefits that take longer than one year to manifest. A primary purpose of the pre period is to ensure precise matching between groups on both the level and trend in key baseline characteristics (e.g., employer characteristics, demographics, utilization patterns, etc.). Our difference-in-difference analyses will include annual-to-annual comparisons (baseline to follow-up year 1, baseline to follow-up year 2, etc.). This will allow intuitive comparisons such as "relative to controls, adherence among HSA-HDHP members with PDLs increased by 4% in follow-up year 1 compared to baseline, but by follow-up year 2, adherence had increased by 11% compared to baseline." We have used this approach in a variety of studies and find that it translates well to clinical and policy audiences. For analyses of outcomes in the second and third year post-switch, we will only include study group patients and their matched controls who have had that length of follow up. We will compare and report differences in baseline characteristics for the subgroups of study cohort members that remain enrolled for each additional year.

We will exclude those over age 64 who are eligible for Medicare. We will identify members with asthma during a 12-24-month period prior to the index date using the same claims-based algorithm used to identify HPHC members with asthma for the Aim 1 interviews, with the inclusion of ICD-9 codes 493.XX to identify a diagnosis of asthma through October 2015. This broad definition will include patients with *intermittent asthma* as well as those with *persistent asthma*, for whom controller medications are recommended. Subgroup analyses will focus on the subset of patients who meet the HEDIS definition of persistent asthma ( $\geq 1$  ED or inpatient visit with asthma as the principal diagnosis,  $\geq 4$  outpatient visits with any asthma diagnosis, or  $\geq 4$  asthma drug dispensing events in the baseline year).

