Eligible employers are those that offer only one plan type in a given benefit year: 1) traditional HMO/PPO/POS plans (deductibles  $<\$1000$ , copayments of  $<\$50$  for most services, tiered copayments for medicines); 2) HSA-HDHPs without PDLs; or 3) HSA-HDHPs with PDLs. We will select “full-replacement” employers that replace a traditional plan with an HSA-HDHP without PDL, or replace an HSA-HDHP without PDL with an HSA-HDHP with PDL, for all employees at a given point in time; matched comparison employers will include those that keep all employees in their prior plan. Including only full-replacement employers is a key strategy used in multiple previous studies to reduce member self-selection bias. The index dates for HSA-HDHP enrollees will be the dates of the employer-mandated plan switch. Matched controls will have contemporaneous enrollment in traditional plans also mandated by their employers; index dates will be assigned to be the same as matched intervention enrollees. We will also include matched controls who remain in HSA-HDHPs without PDLs. To reduce bias due to dropout, we will censor both HDHP and control patients together when either one drops out, and weight the remaining population to retain its baseline demographic and clinical profile. We estimate that there will be 621,481 adults and 310,741 children with asthma from 2004-2017 who will meet our inclusion criteria: 18,000 asthma patients in HSA-HDHPs without PDLs, 4,222 in HSA-HDHPs with PDLs, and 910,000 in traditional plans.

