## **Predictors and Covariates**

Table 2 shows the main predictors and covariates we will use in the proposed study for propensity matching to create study cohorts (CI-1, 4-5), predicting or adjusting outcomes, or stratifying analyses. Our primary predictor variables include study period and insurance type. Study period indicates the one-year period before or up to three years after the index date. Insurance type includes: 1) HSA-HDHP without PDL; 2), HSA-HDHP with PDL; and 3) traditional plan.

Other co-variates include asthma severity in the baseline period using the HEDIS definition for persistent asthma (see above under Study Population), and using chronic oral corticosteroid therapy (180+ days in the prior year) or any use of omalizumab in the baseline year to define severe asthma. To estimate co-morbidity, we will use the well-established Johns Hopkins Adjusted Clinical Groups (ACG) scores which use ICD-10 codes in the baseline period to calculate a standardized morbidity score in a specified time period. We will measure the presence of other chronic conditions from claims data in the baseline year using the Johns Hopkins ACG system. We will also measure whether enrollees have COPD as a co-morbidity, as there can be overlap with COPD and asthma, and use of similar medications.

A unique innovation of our study is the availability of data linkages (IR-2) with consumer data from a

major credit reporting company linked to insurance claims from our data vendor, Optum. Consumer data elements include total household income, net

worth, and race/ethnicity. We will combine self-reported race/ethnicity data from credit card and loan applications with data from Optum on surname analysis for identifying Hispanic or Asian ethnic groups and geocoding to derive race/ethnicity from census data. We will also use census-based indicators for neighborhood education and poverty levels. Other variables used to propensity-match cohorts and adjust for confounding will include sex and age; state/region of residence; individual versus family plan; baseline number of outpatient visits, presence of an inpatient hospitalization, and total expenditures; employer size (number of employees); and average employer baseline expenditures per capita (CI-1, 4-5).

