**Table 2: Predictors and covariates**

| Covariate                         | Use*    | Notes  |
|-----------------------------------|---------|--|
| Study period                      | P       | Pre (1 yr pre), Follow-up (up to 3 yrs post)   |
| Insurance type                    | P       | HSA-HDHP without PDL, HSA-HDHP with PDL, traditional plan  |
| Income                            | P, M, S | Subscriber income in dollars and as a % of Federal Poverty Level (FPL) (<250%, 250-399%, >400%)  |
| Lives in neighborhood with:       |         |  |
| Low education                     | P, M    | ≥25% with less than high school education  |
| High poverty                      | P, M    | ≥10% living below poverty level  |
| Low SES                           | P, M    | Either low education or high poverty   |
| Race/ethnicity                    | P, M, S | Hispanic; Asian; Black; White; Other   |
| Persistent asthma                 | P, S    | Based on HEDIS definition  |
| Severe asthma                     | P, S    | On oral steroids or omalizumab   |
| ACG Score                         | P, M, S | For patient and mean for family; >2 signifies high morbidity                                     |
| Other chronic conditions          | P, M, S | For patient, other family members, from AHRQ Chronic Condition Indicator list                    |
| Region of residence               | M       | State classified into 9 geographic regions   |
| Sex                               | P, M    |  |
| Age on index date                 | M       | For patient; mean for adults and children in family  |
| Adult vs. child                   | P, S    | Age 18-64 vs. age 4-17   |
| Family coverage                   | M       | In a family vs. individual plan  |
| Family size                       | M       | Number sharing same insurance account  |
| Family members with asthma        | P       | Other adults, other children   |
| Number of medications             | P, M    | For baseline year, controller, rescue, other (on and off PDL); for patient, other family members |
| Outpatient visits                 | M       | For baseline year: for patient and mean for family   |
| Hospitalization                   | M       | For baseline year: ≥1 admission, mean per family   |
| Total expenditures                | M       | For baseline year: for patient and mean for family   |
| Employer size                     | M       | 2-50; 51-250; 251-999; ≥1000 employees   |

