| Employer health care expenditures | M       | Per capita, for baseline year  |

\* P=predictors; M=used in propensity matching; S=used to stratify analyses

category; baseline level and trend of total per capita health care expenditure quintile; baseline level and trend of outpatient, ED, and hospital visits quintile; median employee age; median employee ACG score; and percentage of employees who are women, in family plans, and living in lower SES neighborhoods (Table 2). We will perform this employer-level match separately for each intervention group of interest (HSA-HDHPs with and without PDLs) in order to generate each comparison with the control group remaining in traditional plans or HSA-HDHPs without PDLs.

Intervention and control groups will be matched based on their baseline characteristics when both were in the same type of plan. We will set  $p < 0.05$  as a cutoff for including predictors and use backwards selection to choose a parsimonious model, testing for significant effects on remaining predictors when one is eliminated. Following methods in our ongoing work, we will stratify employers based on resulting propensity scores into quartiles. We will then perform individual-level propensity matching within each quartile (below) to develop a multiple control groups for each intervention group.

Within employer propensity quartiles, we will create closely matched control groups using individual-level propensity score matching (CI-1, 4-5), with family-level covariates included in the matching. Using individual and family-level covariates from the baseline period, we will match four contemporaneous control group patients to each intervention group patient within a standard propensity score caliper (0.2 of the standard deviation of the logit of the pooled baseline propensity score). Use of a comparison group matched at both employer- and individual-level will generate study cohorts with nearly identical employer/member demographics and baseline health care trends, offering a further degree of control for any potential changes that may influence specific study outcomes.

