***Hypothesis:** Adults with asthma will disproportionately experience negative effects of HSA-HDHPs on adherence and outcomes relative to children with asthma (HT-2), as will patients who have other family members with asthma or other chronic conditions; differences will be mitigated by the addition of a PDL.*

Aim 3 will focus on intra-familial trade-offs in response to cost-sharing changes in HSA-HDHPs and PDLs, and on adult-child differences in response to HSA-HDHPs and PDLs. Analyses will use the same population, outcomes, study group comparisons, and modeling strategies as Aims 1 and 2 except that we will perform stratified analyses, comparing outcomes between intervention and control groups stratified by adult/child status (RQ-4). To statistically test for heterogeneity of treatment effect for adults vs. children (HT-1-3), we will use three-way interaction terms (insurance type \* study period \* adult/child) to test for statistical differences between adults and children in the impact of the change to an HSA-HDHP with PDL vs. remaining in an HSA-HDHP without PDL, and the change to an HSA-HDHP without PDL vs. remaining in a traditional plan. Analyses will be done at the individual level, but will include family-level variables listed in Table 2 as predictors of interest. Separately for adults and children, we will test the extent to which having another family member with asthma, another chronic condition, or high baseline family ACG morbidity modifies the impact of HDHPs and PDLs on study outcomes for an individual asthma patient. The primary predictor of interest will be the interaction between the family-level variable, study period, and study group.

We will conduct secondary analyses on the subset of families in the study population that have both an adult and child with asthma insured in the same family plan, and will assess whether adults and children within the same family are differentially impacted by HDHPs and PDLs by comparing outcomes between intervention and control groups in separate strata for adults and children (HT- 1-2, IR-5).

**Aim 4:** to examine the impact of HSA-HDHPs with and without PDLs on out-of-pocket (OOP) costs for patients with asthma.

***Hypothesis:** Enrollees with asthma in HSA-HDHPs without PDLs will have higher OOP costs and increased financial burden as measured by the percent of income spent on OOP costs; the addition of a PDL will diminish these adverse outcomes.*

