### **Sample Size and Power**

**Aim 1:** We will conduct qualitative interviews with approximately 60 patients or parents or patients.

**Aims 2-4:** We estimate that there are 1,695 patients with asthma eligible for our study in 2004 in our dataset (12% of HSA-HDHP members), increasing to 2,449 by 2011 (17% of HSA-HDHP members). Projecting current trends, we expect a total of 22,500 HSA-HDHP members with asthma by 2017. Preliminary numbers suggest a third of the cohort will be children under age 18. Based on detailed estimates from our health insurance partners, ~19% of HSA-HDHP members have a PDL. We will have an abundant number of traditional plan members, more than seven times the number in HSA-

HDHPs. Table 3 displays power calculations for pairs of regression models we plan to run for three primary outcomes: controller medication adherence (PDC) (Aims 2-3), and adverse clinical outcomes (rate of asthma-related ED visits or hospitalizations) (Aims 2-3), and OOP costs (Aim 4), both overall and for stratified analyses by adult/child (power calculations for children are displayed, as they are the smaller group). Power calculations, which assume 80% power and 0.05 alpha level, were performed using PASS software.

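### The individual propensity match is not made within adults and children separately, yet Aim 3 splits the matched population by age group, so balance among children is neither secured nor checked

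*Combined protocol and SAP*

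**What the plan says.** All references are to the combined protocol and SAP, section C.

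- **Matching variables** (Predictors and Covariates): "Other variables used to propensity-match cohorts and adjust for confounding will include sex and age". Table 2 marks age on the index date M (used in propensity matching). The Adult vs. child row, defined as "Age 18-64 vs. age 4-17", is marked P and S (predictor, stratifier) with no M.
- **Individual match** (text after Table 2): within employer-propensity quartiles, "we will match four contemporaneous control group patients to each intervention group patient within a standard propensity score caliper". No other matching stratum is named. The only separation stated is by intervention group, and that sentence concerns the employer-level match.
- **Aim 3** (Analysis plan): it reuses the earlier population, comparisons and models, but with stratified analyses, "comparing outcomes between intervention and control groups stratified by adult/child status", and a three-way interaction of insurance type, study period and adult/child.
- **Follow-up** (Study Population): for years two and three, "we will only include study group patients and their matched controls who have had that length of follow up". The same section and Generalizability and Limitations censor matched patients together when one drops out and re-weight those who remain to the baseline profile.
- **Power**: Table 3 has a column for children.

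The plan does not mention exact matching on age group, separate scores, re-matching for Aim 3, or a balance check within children.

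**The concern.** The difference between adults and children is the first part of the Aim 3 hypothesis. The Analysis plan relies on the match to give intervention and control groups similar baseline trends before difference-in-differences is applied. A match on a score shared by adults and children aims at that property for the whole cohort. It delivers it within children only if the score model is adequate for children. A model without age-group interactions may not be: plan type, family size, expenditures and medication counts could relate to switching differently for a dependent child than for an employee. That mechanism is plausible, but the documents do not establish it.

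Two things are at stake. Imbalance among children could be offset by the opposite imbalance among adults, so an overall balance table would look clean while the child estimate and the interaction were affected. And if sets mix ages, joint censoring makes a child's follow-up depend on an adult's enrolment. The second problem needs no misspecified score.

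**Working it through.** **1. Table 3's child column.** "Power calculations, which assume 80% power and 0.05 alpha level, were performed using PASS software". Child share: "Preliminary numbers suggest a third of the cohort will be children under age 18", which agrees with "621,481 adults and 310,741 children with asthma from 2004-2017": 310,741 / (310,741 + 621,481) = 0.333.

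Dividing the overall column by √(1/3) = 0.577 gives:

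| Outcome | Contrast | Overall | Overall / 0.577 | Stated for children |
|---|---|---|---|---|
| PDC | with PDL | 2.0% | 3.46% | 3.5% |
| PDC | without PDL | 1.0% | 1.73% | 1.7% |
| ED/hospital | with PDL | 1.2% | 2.08% | 2.0% |
| ED/hospital | without PDL | 0.6% | 1.04% | 1.0% |
| OOP | with PDL | $47 | $81 | $80 |
| OOP | without PDL | $23 | $40 | $40 |

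So the child column takes one third of each arm, about 1,407 vs 5,629 and 6,000 vs 24,000. The PDC cells cannot be rebuilt from the stated inputs: treating 46% as a proportion, two-sided, gives 4.2% / 2.0% for children. They imply an SD of about 0.41 to 0.43, which is not stated. With SD 0.42, 2.80 × 0.42 × √(1.25/1,407) = 3.5% and 2.80 × 0.42 × √(1.25/6,000) = 1.7%. This does not show the cells to be wrong.

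**2. Age mix of a child's four controls.** If the score carries no age information, each control is an adult with probability 2/3. The expected number of child controls is 4 × 1/3 = 1.33; P(none) = (2/3)⁴ = 0.20; P(all four) = (1/3)⁴ = 0.01.

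**3. Simulation.** All inputs are assumptions, not document figures: 150,000 people, one third children; age entered linearly plus four covariates; greedy 1:4 nearest-neighbour matching without replacement; caliper 0.2 SD of the logit; no employer quartiles. SMD is the largest absolute standardized mean difference among children.

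| Child effect on switching (log-odds) | Omitted child × covariate term | Adults among a child's controls | Child controls per child, whole matched sample | SMD, shared score | SMD, child-only score |
|---|---|---|---|---|---|
| 0 | 0 | 68% | 4.0 | 0.06 | 0.02 |
| 0.3 | 0 | 68% | 3.7 | 0.04 | 0.02 |
| −0.5 | 0 | 63% | 4.8 | 0.06 | 0.03 |
| 1 | 0 | 51% | 3.3 | 0.04 | 0.01 |
| 2 | 0 | 24% | 3.3 | 0.04 | 0.01 |
| 0 | +0.3 | 70% | 4.0 | 0.20 | 0.02 |
| 0 | −0.4 | 67% | 3.9 | 0.26 | 0.02 |

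A separate simulation assumed a covariate effect of +0.3 in adults and −0.1 in children (log-odds per SD). The overall standardized difference was about 0 and the within-child difference was −0.25 to −0.34. Matching exactly with a child score brought it below 0.03 and lost at most one child.

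**4. Effect on child power.** Child controls per child across the whole matched sample stay at 3.3 to 4.8. Relative to 4, the detectable difference changes by √((1 + 1/3.3)/1.25) = 1.02 to √((1 + 1/4.8)/1.25) = 0.98, so 3.5% becomes 3.4% to 3.6%.

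**The case against.** The case against is substantial, and most of it limits how far the point reaches.

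- **A single score for all ages is never stated.** It is the natural reading, but the word pooled in the caliper definition describes the score whose SD sets the caliper and need not mean adults and children combined.
- **A reader might infer that a child's controls are mostly adults.** That depends on how strongly age predicts switching: the simulated share runs from 24% to 70%, and the documents give no age effect. Age, family ages, family size and plan type all enter the match and may carry age information.
- **A reader might infer that splitting matched sets invalidates the child analysis.** It does not. The named models (GLM, GEE, GLMM, negative binomial) are not described as conditioning on the set.
- **A reader might infer that Table 3 overstates child power.** The column needs about one third of each arm in total, and step 4 shows that this roughly holds. Only an analysis confined to same-set child controls would lose much: information falls to about 60%, and 3.5% / 1.7% becomes about 4.5% / 2.2% (factor 1/√0.60 = 1.29). No such analysis is planned.
- **The imbalance rests on assumed interactions.** Switching is imposed by full-replacement employers on all employees, which leaves less room for individual-level selection. Difference-in-differences removes stable level differences on the model scale. All models adjust for key Table 2 predictors, and separately fitted strata would have child-specific coefficients.
- **Joint censoring is accompanied by re-weighting**, and no bias from it has been shown.

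What stands is that the plan stratifies on a variable it does not match on, does not look at balance within its strata, and leaves censoring free to cross age groups. The defences make bias smaller or less likely, but none of them would reveal it.

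**Conclusion.** The point holds as a gap in design and checking, not as a demonstrated bias. Balance and parallel baseline trends among children are left to the adequacy of a score that, on the natural reading, is shared with adults. If predictors of switching act alike in both groups, the shared match serves children well (SMD 0.04 to 0.06). If they differ by the amounts assumed here, the SMD is about 0.2 to 0.3 and an overall balance table can miss it. A bias in PDC, ED visits or costs would also require the imbalanced covariates to drive differential change after adjustment, and nothing here puts a size on that. Cross-age censoring follows directly from the stated rules wherever sets mix ages. Aim 2, which deliberately analyses adults and children together, is not affected by this point.

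**What to change.** In both contrasts, estimate the individual-level score separately for adults (18–64) and children (4–17) at the index date, and match exactly on that group within employer quartiles. Add M to the Adult vs. child row of Table 2. Report standardized differences and baseline outcome trends for adults and children separately, beside the overall table. Matched sets then stay within one age group, so a child can no longer be censored because an adult control disenrolled.

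The cost is SAP wording and a re-run of the match. The traditional-plan contrast draws on about 910,000 potential controls, so little should be lost there. In the PDL contrast the pool is smaller and some children may have fewer than four controls; report how many. Table 3 needs no change on this account. If the match cannot be re-run, the minimum is to report the within-child balance and baseline trends.

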**Table 2: Predictors and covariates**

| Covariate                         | Use*    | Notes  |
|-----------------------------------|---------|--|
| Study period                      | P       | Pre (1 yr pre), Follow-up (up to 3 yrs post)   |
| Insurance type                    | P       | HSA-HDHP without PDL, HSA-HDHP with PDL, traditional plan  |
| Income                            | P, M, S | Subscriber income in dollars and as a % of Federal Poverty Level (FPL) (<250%, 250-399%, >400%)  |
| Lives in neighborhood with:       |         |  |
| Low education                     | P, M    | ≥25% with less than high school education  |
| High poverty                      | P, M    | ≥10% living below poverty level  |
| Low SES                           | P, M    | Either low education or high poverty   |
| Race/ethnicity                    | P, M, S | Hispanic; Asian; Black; White; Other   |
| Persistent asthma                 | P, S    | Based on HEDIS definition  |
| Severe asthma                     | P, S    | On oral steroids or omalizumab   |
| ACG Score                         | P, M, S | For patient and mean for family; >2 signifies high morbidity                                     |
| Other chronic conditions          | P, M, S | For patient, other family members, from AHRQ Chronic Condition Indicator list                    |
| Region of residence               | M       | State classified into 9 geographic regions   |
| Sex                               | P, M    |  |
| Age on index date                 | M       | For patient; mean for adults and children in family  |
| Adult vs. child                   | P, S    | Age 18-64 vs. age 4-17   |
| Family coverage                   | M       | In a family vs. individual plan  |
| Family size                       | M       | Number sharing same insurance account  |
| Family members with asthma        | P       | Other adults, other children   |
| Number of medications             | P, M    | For baseline year, controller, rescue, other (on and off PDL); for patient, other family members |
| Outpatient visits                 | M       | For baseline year: for patient and mean for family   |
| Hospitalization                   | M       | For baseline year: ≥1 admission, mean per family   |
| Total expenditures                | M       | For baseline year: for patient and mean for family   |
| Employer size                     | M       | 2-50; 51-250; 251-999; ≥1000 employees   |
| Employer health care expenditures | M       | Per capita, for baseline year  |

\* P=predictors; M=used in propensity matching; S=used to stratify analyses

category; baseline level and trend of total per capita health care expenditure quintile; baseline level and trend of outpatient, ED, and hospital visits quintile; median employee age; median employee ACG score; and percentage of employees who are women, in family plans, and living in lower SES neighborhoods (Table 2). We will perform this employer-level match separately for each intervention group of interest (HSA-HDHPs with and without PDLs) in order to generate each comparison with the control group remaining in traditional plans or HSA-HDHPs without PDLs.

Intervention and control groups will be matched based on their baseline characteristics when both were in the same type of plan. We will set  $p < 0.05$  as a cutoff for including predictors and use backwards selection to choose a parsimonious model, testing for significant effects on remaining predictors when one is eliminated. Following methods in our ongoing work, we will stratify employers based on resulting propensity scores into quartiles. We will then perform individual-level propensity matching within each quartile (below) to develop a multiple control groups for each intervention group.

Within employer propensity quartiles, we will create closely matched control groups using individual-level propensity score matching (CI-1, 4-5), with family-level covariates included in the matching. Using individual and family-level covariates from the baseline period, we will match four contemporaneous control group patients to each intervention group patient within a standard propensity score caliper (0.2 of the standard deviation of the logit of the pooled baseline propensity score). Use of a comparison group matched at both employer- and individual-level will generate study cohorts with nearly identical employer/member demographics and baseline health care trends, offering a further degree of control for any potential changes that may influence specific study outcomes.

